## 10. Final Power Assessment

Date conducted: 12/01/2019

- Re-calculate power in the appropriate excel table, using the revised number of matched patients from the PS-match in Section 9. All other parameters in the table should be the same as in Section 8. If the study is to be implemented in more than one database, copy and paste excel sheet to report power for each database separately and for the pooled analysis that uses data

from all databases together. Power calculations are based on the formulas from Chow et al. (2008).

- For Liraglutide vs DPP4i

- Pooled

Superiority Analysis		Non-inferiority Analysis	
Number of patients matched		Number of patients matched	
Reference	84,345	Reference	84,345
Exposed	84,345	Exposed	84,345
Risk per 1,000 patients	21.67	Risk per 1,000 patients	21.67
Desired HR from RCT	0.87	Assumed HR from RCT	1
Alpha (2-sided)	0.05	Alpha (2-sided)	0.05
		Non-inferiority margin	1.3
Number of events expected	3655.5123	Number of events expected	3655.5123
Power	0.987775093	Power	0.999999999

- Optum

Superiority Analysis		Non-inferiority Analysis	
Number of patients matched		Number of patients matched	
Reference	19,187	Reference	19,187
Exposed	19,187	Exposed	19,187
Risk per 1,000 patients	14.30	Risk per 1,000 patients	14.30
Desired HR from RCT	0.87	Assumed HR from RCT	1
Alpha (2-sided)	0.05	Alpha (2-sided)	0.05
		Non-inferiority margin	1.3
Number of events expected	548.7482	Number of events expected	548.7482
Power	0.371306397	Power	0.867151513

▪ Marketscan

Superiority Analysis		Non-inferiority Analysis	
Number of patients matched		Number of patients matched	
Reference	20,777	Reference	20,777
Exposed	20,777	Exposed	20,777
Risk per 1,000 patients	12.11	Risk per 1,000 patients	12.11
Desired HR from RCT	0.87	Assumed HR from RCT	1
Alpha (2-sided)	0.05	Alpha (2-sided)	0.05
		Non-inferiority margin	1.3
Number of events expected	503.21894	Number of events expected	503.21894
Power	0.345542948	Power	0.837143294

▪ Medicare

Superiority Analysis		Non-inferiority Analysis	
Number of patients matched		Number of patients matched	
Reference	44,381	Reference	44,381
Exposed	44,381	Exposed	44,381
Risk per 1,000 patients	38.60	Risk per 1,000 patients	38.60
Desired HR from RCT	0.87	Assumed HR from RCT	1
Alpha (2-sided)	0.05	Alpha (2-sided)	0.05
		Non-inferiority margin	1.3
Number of events expected	3426.2132	Number of events expected	3426.2132
Power	0.982819492	Power	0.999999995

- o For Liraglutide vs 2nd Gen. SUs

- Pooled

Superiority Analysis		Non-inferiority Analysis	
Number of patients matched		Number of patients matched	
Reference	54,182	Reference	54,182
Exposed	54,182	Exposed	54,182
Risk per 1,000 patients	30.10	Risk per 1,000 patients	30.1
Desired HR from RCT	0.87	Assumed HR from RCT	1
Alpha (2-sided)	0.05	Alpha (2-sided)	0.05
		Non-inferiority margin	1.3
Number of events expected	3261.7564	Number of events expected	3261.7564
Power	0.978141227	Power	0.999999984

- Optum

Superiority Analysis		Non-inferiority Analysis	
Number of patients matched		Number of patients matched	
Reference	12,253	Reference	12,253
Exposed	12,253	Exposed	12,253
Risk per 1,000 patients	18.97	Risk per 1,000 patients	18.97
Desired HR from RCT	0.87	Assumed HR from RCT	1
Alpha (2-sided)	0.05	Alpha (2-sided)	0.05
		Non-inferiority margin	1.3
Number of events expected	464.87882	Number of events expected	464.87882
Power	0.323513047	Power	0.807428816

▪ Marketscan

Superiority Analysis		Non-inferiority Analysis	
Number of patients matched		Number of patients matched	
Reference	13,591	Reference	13,591
Exposed	13,591	Exposed	13,591
Risk per 1,000 patients	22.54	Risk per 1,000 patients	22.54
Desired HR from RCT	0.87	Assumed HR from RCT	1
Alpha (2-sided)	0.05	Alpha (2-sided)	0.05
		Non-inferiority margin	1.3
Number of events expected	612.68228	Number of events expected	612.68228
Power	0.406665538	Power	0.900972235

▪ Medicare

Superiority Analysis		Non-inferiority Analysis	
Number of patients matched		Number of patients matched	
Reference	28,338	Reference	28,338
Exposed	28,338	Exposed	28,338
Risk per 1,000 patients	48.79	Risk per 1,000 patients	48.79
Desired HR from RCT	0.87	Assumed HR from RCT	1
Alpha (2-sided)	0.05	Alpha (2-sided)	0.05
		Non-inferiority margin	1.3
Number of events expected	2765.22204	Number of events expected	2765.22204
Power	0.955585785	Power	0.999999606

- Stop analyses until balance and final power assessment are reviewed by primary investigators, FDA, and assigned members of advisory board. Reviewers evaluate the results of the analyses described above in Sections 9 and 10, including numbers of patients, balance in patient characteristics, follow-up time, and reasons for censoring by treatment group, as well as overall rates of outcomes and study power.

Reviewed by PI:	[name]	Date reviewed:	12/9/19
Reviewed by FDA:	[name]	Date reviewed:	12/20/19
Reasons for stopping analysis (if required):			

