### 1.4 Required power for primary endpoint and noninferiority margin (if applicable)

90% power and noninferiority margin of hazard ratio of 1.30

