## 9. Balance Assessment after PS matching

Action report name:

- For Liraglutide vs 2nd Gen. SUs

Optum: <https://bwh-dope.aetion.com/projects/details/632/results/44783/result/0>

Marketscan: <https://bwh-dope.aetion.com/projects/details/633/results/45436/result/0>

Medicare: <https://bwh-dope.aetion.com/projects/details/634/results/45432/result/0>

- For Liraglutide vs DPP4i

Optum: <https://bwh-dope.aetion.com/projects/details/632/results/44786/result/0>

Marketscan: <https://bwh-dope.aetion.com/projects/details/633/results/44787/result/0>

Medicare: <https://bwh-dope.aetion.com/projects/details/634/results/45433/result/0>

Date conducted: 11/18/2019 (Medicare 11/30/2019)

After review of initial feasibility and power analyses, complete creation of the remaining covariates (see Table 1 below for list of covariates). Again, using the dummy outcome of a 90-day gap in database enrollment, complete a 1:1 PS-matched analysis. The PS should include the complete list of covariates (excluding laboratory values, which are missing in some patients).

- Provide plot of PS distributions stratified by treatment group.

Note- Please refer to **Appendix B**.

- Report covariate balance after matching.

Note- For Table 1, please refer to **Appendix B**.

- Report reasons for censoring by treatment group.

- For Liraglutide vs DPP4i

	Overall	Referent	Exposure
Dummy Outcome	0 (0.00%)	0 (0.00%)	0 (0.00%)
Death	1,271 (0.75%)	827 (0.98%)	444 (0.53%)
Start of an additional exposure	4,700 (2.79%)	1,913 (2.27%)	2,787 (3.30%)

End of index exposure	99,981 (59.27%)	45,078 (53.44%)	54,903 (65.09%)
Specified date reached	29,951 (17.76%)	16,708 (19.81%)	13,243 (15.70%)
End of patient enrollment	22,798 (13.51%)	12,483 (14.80%)	10,315 (12.23%)
Switch to other SUs (for censoring) + nursing home admission	9,989 (5.92%)	7,336 (8.70%)	2,653 (3.15%)

- For Liraglutide vs 2nd Gen. SUs

	Overall	Referent	Exposure
Dummy Outcome	0 (0.00%)	0 (0.00%)	0 (0.00%)
Death	858 (0.79%)	595 (1.10%)	263 (0.49%)
Start of an additional exposure	4,294 (3.96%)	967 (1.78%)	3,327 (6.14%)
End of index exposure	61,038 (56.33%)	27,098 (50.01%)	33,940 (62.64%)
Specified date reached	21,830 (20.15%)	13,222 (24.40%)	8,608 (15.89%)
End of patient enrollment	14,181 (13.09%)	7,902 (14.58%)	6,279 (11.59%)
Switch to other SUs (for censoring) + nursing home admission	6,163 (5.69%)	4,398 (8.12%)	1,765 (3.26%)

- Report follow-up time by treatment group.

- For Liraglutide vs DPP4i

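### Pooled expected events in Section 10 fall 15–18% short of the sum of the database tables beneath them; the error is conservative and minor

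*Combined protocol and SAP*

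**What the plan says.** Section 10 (Final Power Assessment) instructs the team to "report power for each database separately and for the pooled analysis that uses data" from all databases combined, using the matched numbers from Section 9. It adds: "All other parameters in the table should be the same as in Section 8". The Section 9 comparison is 1:1 ("complete a 1:1 PS-matched analysis").

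For each comparator, Section 10 prints a pooled table followed by one table each for Optum, MarketScan and Medicare. Each table gives the matched N per arm, a risk per 1,000 patients, the expected events and the power. The database risks also appear at the end of Section 9. The pooled risk is entered as 21.67 for DPP4i and 30.10 for second-generation sulfonylureas. Neither section says how these two values were obtained.

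The section ends with a stop for review, at which reviewers consider balance, follow-up and censoring, "as well as overall rates of outcomes and study power". Section 1.4 sets the benchmark: "90% power and noninferiority margin of hazard ratio of 1.30".

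**The concern.** The pooled tables describe the same matched patients as the three database tables beneath them, because the Ns add exactly. Expected events must therefore add as well, and they do not.

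The pooled outcome rate and the pooled power are among the quantities reviewers are asked to judge before the analysis proceeds. Section 12 then has the document uploaded to a public registry. A reader who later compared the observed pooled events with the plan would be using a benchmark that does not agree with the plan's own database figures.

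**Working it through.** **Inputs (Section 10; the database risks also in Section 9)**

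| Comparator | Table | N per arm | Risk per 1,000 | Events stated |
|---|---|---|---|---|
| DPP4i | Optum | 19,187 | 14.30 | 548.7482 |
| DPP4i | MarketScan | 20,777 | 12.11 | 503.21894 |
| DPP4i | Medicare | 44,381 | 38.60 | 3,426.2132 |
| DPP4i | Pooled | 84,345 | 21.67 | 3,655.5123 |
| SU | Optum | 12,253 | 18.97 | 464.87882 |
| SU | MarketScan | 13,591 | 22.54 | 612.68228 |
| SU | Medicare | 28,338 | 48.79 | 2,765.22204 |
| SU | Pooled | 54,182 | 30.10 | 3,261.7564 |

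Hazard ratio 0.87 for superiority; hazard ratio 1 with margin 1.3 for non-inferiority; two-sided alpha 0.05; 1:1 allocation.

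**Step 1: reproduce the plan's figures.** Events d = 2 × N × risk / 1000 gives every stated count exactly, including the pooled ones: 2 × 84,345 × 21.67 / 1000 = 3,655.5123 and 2 × 54,182 × 30.10 / 1000 = 3,261.7564. For power:

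- Superiority: Φ(t − 1.96) + Φ(−t − 1.96), with t = √d × |ln 0.87| / 2.
- Non-inferiority: Φ(√d × ln 1.3 / 2 − 1.96).

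These reproduce all 16 stated powers to within 1e-9. At d = 3,655.5, for example, t = 60.461 × 0.13926 / 2 = 4.210 and power is Φ(2.250) = 0.9878. The formulas and the multiplication are therefore sound, and the only input left to question is the pooled risk.

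**Step 2: check that the rows add.**

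- N, DPP4i: 19,187 + 20,777 + 44,381 = 84,345, as stated.
- N, SU: 12,253 + 13,591 + 28,338 = 54,182, as stated.
- Events, DPP4i: 548.748 + 503.219 + 3,426.213 = 4,478.180, against 3,655.512 stated. The shortfall is 822.668, or 18.4% of the sum.
- Events, SU: 464.879 + 612.682 + 2,765.222 = 3,842.783, against 3,261.756 stated. The shortfall is 581.027, or 15.1%.

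Seen another way, subtracting Medicare's own events from the DPP4i pooled total leaves 3,655.5 − 3,426.2 = 229.3 events for Optum and MarketScan together, whose own tables give 548.7 + 503.2 = 1,052.0. Rounding cannot account for that.

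**Step 3: where the pooled risk comes from.**

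- Unweighted means: (14.30 + 12.11 + 38.60) / 3 = 21.67 and (18.97 + 22.54 + 48.79) / 3 = 30.10. Both match the table to every printed digit.
- Weighted by matched N: 4,478.180 / (2 × 84,345) = 26.55 per 1,000 and 3,842.783 / (2 × 54,182) = 35.46 per 1,000.

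An unweighted mean gives Medicare, the highest-risk source, a weight of one third. It actually holds 44,381 / 84,345 = 52.6% and 28,338 / 54,182 = 52.3% of the matched patients.

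**Step 4: power at the row sums.**

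- DPP4i: t = 66.919 × 0.13926 / 2 = 4.660; superiority power Φ(2.700) = 0.9965 (stated 0.9878, a rise of 0.9 points).
- SU: t = 61.990 × 0.13926 / 2 = 4.316; superiority power Φ(2.356) = 0.9908 (stated 0.9781, a rise of 1.3 points).
- Non-inferiority, 1 − power: from 1.2e-9 to 4.6e-12 (DPP4i) and from 1.6e-8 to 3.4e-10 (SU).

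**The case against.** The strongest objection is that nothing turns on this. The error understates power, the requirement in Section 1.4 is met either way, and pooled non-inferiority power is already indistinguishable from 1. The database figures are printed directly below each pooled table, where any reviewer could add them up. This stands in full; it limits the grade to minor and gives no reason to think the review was compromised.

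A second objection is that Section 10 carries every parameter except matched N over from Section 8, so the pooled risk may simply have been inherited. Section 8 prints no risk values, so this cannot be checked. It would not help in any case, because the database tables in Section 10 apply their risks to the updated Ns and imply the larger totals.

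A third is that the replacement figures assume the database risks in Section 9 apply to the final matched cohorts. Report links dated 04/25/2019 follow those risks, whereas the matching is dated 11/18/2019 (Medicare 11/30/2019), and it is unclear whether the April reports are their source. The caveat on the restated values is fair. It does not rescue the pooled entries, since the six database tables use those same risks and still add to different totals.

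**Conclusion.** The pooled tables are wrong as written. Given the plan's own database risks and matched Ns, expected events are understated by 822.7 (DPP4i) and 581.0 (sulfonylureas), and superiority power by 0.9 and 1.3 percentage points. The internal contradiction does not depend on how it arose. Unweighted averaging of the database risks is an inference, although it fits both comparisons exactly. The error is conservative and confined to the two pooled tables. It affects neither the six single-database tables nor the decision to proceed. Minor.

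**What to change.** In both panels of each pooled table, set expected events to the sum of the database rows: 4,478.2 (DPP4i) and 3,842.8 (sulfonylureas). Show the matching patient-weighted risks, 26.55 and 35.46 per 1,000. Use the row sums for the calculation, because the rounded risks give 2 × 84,345 × 26.55 / 1000 = 4,478.7 and 2 × 54,182 × 35.46 / 1000 = 3,842.6; power to four decimals is the same apart from rounding in the last digit.

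Restate superiority power as 0.9965 (DPP4i) and 0.9908 (sulfonylureas), and non-inferiority power as above 0.9999 in both. Add one sentence saying how the pooled risk is derived and which run the database risks come from. Leave the single-database tables alone.

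The cost is four risk entries and the eight event and power cells that depend on them. There is no design change and no new data run.

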## 11. Study Confidence and Concerns

Deadline for voting on study confidence and listing concerns: 12/20/19

- If final feasibility and power analyses are reviewed and approved, proceed to the remaining protocol steps.
- All study team and advisory board members that review this protocol should at this stage provide their level of confidence for the success of the RWD study in the [Google Form](#). This form also provides space for reviewers to list any concerns that they feel may contribute to a failure to replicate the findings of the RCT, including differences in study populations, poor measurement of study

variables, or residual confounding. All responses will be kept confidential and individual-level results will only be shared with the individual respondent.

## **12. Register study protocol on clinicalTrials.gov**

Date conducted:

- Register the study on [clinicalTrials.gov](https://clinicaltrials.gov) and upload this document.

## **13. Comparative Analyses**

Action report name:

Date conducted:

### **13.1 For primary analysis:**

- In the PS-matched cohort from Section 9, calculate the HR for each outcome for liraglutide versus 2nd generation SU patients using a Cox proportional hazards model.

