##### Design Diagram – LEADER TRIAL REPLICATION

## 5. Cohort Identification

### 5.1 Cohort Summary

This study will involve a new user, parallel group, cohort study design comparing liraglutide to the DPP4 inhibitor (DPP4i) antidiabetic class as a proxy for placebo. Both 2nd generation sulfonylureas (SUs) and DPP4is are not known to have an impact on the outcome of interest. The comparison against DPP4i is the **primary comparison**. Initiators of 2nd generation SUs are used as a secondary comparator group. The patients will be required to have continuous enrollment during the baseline period of 180 days before initiation of liraglutide or a comparator drug (cohort entry date). Follow-up for the outcome (3P-MACE), begins the day after drug initiation. As in the trial, patients are allowed to take other antidiabetic medications during the study.

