## 6. Variables

### 6.1 Exposure-related variables:

#### Study drug:

The study exposure of interest is initiation of liraglutide. Initiation will be defined by no use of liraglutide or a comparator in the prior 6 months before treatment initiation (washout period).

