#### Comparator agents:

- Initiators of liraglutide will be compared to initiators of-
  - DPP4i (**primary**)
  - 2nd generation sulfonylureas

Because liraglutide and comparators are frequently used as second or third line treatments of T2DM, we expect it to be unlikely that liraglutide and comparators are initiated in patients with substantially different baseline risk for proposed outcomes.

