### **13.2 For secondary analyses:**

- In the PS-matched cohort from Section 9, calculate the HR for each outcome for liraglutide versus DPP4i patients using a Cox proportional hazards model.
- In both pre-matched cohorts, perform asymmetrical trimming to remove patients with PS values below the 2.5th percentile of treated patients and above the 97.5th percentile of untreated patients. In the trimmed cohort, calculate the HR for canagliflozin versus referent patients using a Cox proportional hazards model, adjusting for deciles of the PS.

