## **14. Requested Results**

#### 14.1 Results from primary and secondary analyses:

Separately for each endpoint and each comparator group:

Analysis	No. exposed events	No. referent events	Exposed rate	Referent rate	HR (95% CI)
Crude					
Primary analysis					
Analysis 2					
...					

HR, Hazard Ratio; CI, Confidence Interval.

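### Section 13 swaps the primary and secondary comparators set in Sections 5.1 and 6.1, and its trimmed analysis names a drug that is not under study

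*Combined protocol and SAP*

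**What the plan says.** Section 5.1 names DPP4 inhibitors as the proxy for placebo, declares that comparison primary, and says that initiators of 2nd "generation SUs are used as a secondary comparator group". The comparator list in Section 6.1 marks DPP4i as primary again.

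Section 13 tells the analyst what to run. Under its primary-analysis heading, 13.1 asks for the hazard ratio of liraglutide against 2nd "generation SU patients using a Cox proportional hazards model". Under its secondary-analyses heading, 13.2 asks the analyst to "calculate the HR for each outcome for liraglutide versus DPP4i patients using a Cox proportional hazards model".

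A further item in 13.2 trims both pre-match cohorts on the propensity score and says to "calculate the HR for canagliflozin versus referent patients using a Cox proportional hazards model". Section 6.1 is clear on the exposure: "The study exposure of interest is initiation of liraglutide".

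**The concern.** The analysis section contradicts the design sections on which comparison is primary. Followed as written, it makes the SU hazard ratio the primary result to set against the trial estimate in Section 1.5 (HR 0.87, 95% CI 0.78 to 0.97), although the design chose DPP4i for that role. Section 12 says this document is to be uploaded to the registry. The registered plan would then support either hazard ratio as primary, and the choice could be made after both are known.

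The two results are not interchangeable. They rest on different matched cohorts, and the liraglutide arm itself differs between them.

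The canagliflozin wording is a separate and smaller error. It affects one secondary analysis and has no bearing on which comparator is primary.

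**Working it through.** **Roles, side by side**

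| Section | DPP4i | 2nd-generation SU |
|---|---|---|
| 5.1 | primary | secondary |
| 6.1 | primary | listed without that mark |
| 13.1 and 13.2 | secondary | primary |

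Section 14.1 does not settle the matter. Its results table is to be completed "Separately for each endpoint and each comparator group", and the shell has a row for the primary analysis, so each comparator produces a row with that label.

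**The plan's own figures (Section 10, pooled)**

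Expected events = 2 × pairs × risk per 1,000 / 1,000.

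- DPP4i: 2 × 84,345 × 21.67 / 1,000 = 3,655.5
- SU: 2 × 54,182 × 30.10 / 1,000 = 3,261.8

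Superiority power = Φ(|ln HR| × √events / 2 − 1.96), with HR 0.87 and two-sided alpha 0.05.

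- DPP4i: 0.1393 × 60.46 / 2 − 1.96 = 2.25, power 0.9878 (stated 0.987775)
- SU: 0.1393 × 57.11 / 2 − 1.96 = 2.02, power 0.9781 (stated 0.978141)

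Both stated values reproduce. Non-inferiority power exceeds 0.9999 for both.

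**How far the cohorts differ**

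- Pairs: 84,345 − 54,182 = 30,163 fewer for SU; 30,163 / 84,345 = 35.8%.
- SU use among matched liraglutide patients in the DPP4i cohort (Appendix B, Table 1, Liraglutide vs DPP4i, PS-matched; Optum + MarketScan + Medicare):
  - concomitant or current: 5,716 + 6,177 + 14,751 = 26,644
  - past: 1,517 + 1,699 + 3,827 = 7,043
  - total: 33,687; 33,687 / 84,345 = 39.9%
- By database: Optum 7,233 / 19,187 = 37.7%; MarketScan 7,876 / 20,777 = 37.9%; Medicare 18,578 / 44,381 = 41.9%.

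Adding the two categories assumes that they do not overlap. The table gives no overall SU row to test this, but the same split adds up exactly elsewhere in that arm: insulin 9,179 + 6,132 = 15,311 and metformin 44,759 + 10,266 = 55,025, each equal to the overall medication row.

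Section 6.1 defines initiation by "no use of liraglutide or a comparator in the prior 6 months before treatment initiation". The flowcharts in Section 5.3 apply this cohort by cohort, removing prior users of that cohort's reference drug. A separate row removes patients who qualify for both drugs (138 + 236 + 85 = 459 in the SU flowchart). The 33,687 patients therefore could not enter the SU cohort at that index date.

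**Cross-check on unmatched liraglutide counts**

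- DPP4i cohort less SU users: 85,279 − 26,745 − 7,083 = 51,451
- Add past (2,542) and concomitant or current (109 + 124 + 225 = 458) DPP4i users, who appear only in the SU cohort: 54,451
- Reported SU cohort: 54,804, a difference of 353 (0.6%)

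**Balance on variables outside the propensity score**

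Section 9 leaves laboratory values out of the model. After SU matching, pooled mean HbA1c is 8.10 against 7.86 (standardized difference 0.13). After DPP4i matching it is 8.05 against 8.03 in Optum and 8.02 against 8.03 in MarketScan (0.01 and −0.01). HbA1c is available for only about a fifth of Optum and MarketScan patients and for none in Medicare, so this is supporting evidence only.

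**The case against.** The best defence is that no analysis is lost. Sections 13.1 and 13.2 prescribe the same matched Cox model for both comparators, Section 14.1 asks for results for each, and no alpha split or testing hierarchy depends on the label. The intent is also fairly plain: two design sections agree, and the section that disagrees contains another slip. On precision, pairs exaggerate the contrast. Events fall by 10.8% (3,655.5 to 3,261.8), and the approximate standard error of the log hazard ratio, 2/√events, rises from 0.0331 to 0.0350, about 6%. The 35.8% and 39.9% describe two planned cohorts and are the same before and after any correction.

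All of that is accurate, and it limits the point to designation: there is no missing analysis and no shortage of pooled power. It does not remove the contradiction. Readers may infer that DPP4i was meant, but the instruction to the analyst says otherwise, and prespecification should not rest on inference. The cohort figures show why the label has consequences: the two hazard ratios describe materially different liraglutide populations.

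Read alone, the Section 6.1 washout could bar both comparator classes from both cohorts. The flowcharts, and the SU users present in the DPP4i table, show that it was applied by cohort.

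**Conclusion.** The concern holds. Section 13 contradicts Sections 5.1 and 6.1 on the primary comparator, no text reconciles them, and the primary result is not uniquely defined. As written, 13.1 gives primary status to a comparison with 35.8% fewer pairs, which leaves out about two in five of the liraglutide patients behind the declared primary comparison. The 39.9% rests on current and past SU use being non-overlapping and on the cohort-specific washout shown in the flowcharts. The size of any resulting difference between the two hazard ratios cannot be judged from the document. The wrong drug name in 13.2 is confirmed as a separate, minor error. The contradiction must be corrected before the comparative analyses are run.

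**What to change.** Name liraglutide versus DPP4i as the primary analysis in Section 13.1 and move liraglutide versus second-generation SU to Section 13.2, in line with Sections 5.1 and 6.1. In the trimmed, decile-adjusted analysis, replace canagliflozin with liraglutide; the text already applies that analysis to both cohorts.

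The cost is a wording change in Section 13. No data, analysis or power figure changes. The dates in Sections 12 and 13 are blank, so on the face of the document the correction can still be made before registration and before any comparative result is seen.
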